4.12 ETHICAL ISSUES AND CONSENT ACQUIREMENT PROCESS

Since this study involves the use of invasive interventions on human subjects, it therefore requires ethical review of study protocol by the institutional review board. To meet this requirement, an ethical clearance was sought from USM Human Research Ethics Committee, which was obtained on **20th June 2016 (Human Research Ethics Committee (HREC) reference number: USM/JEPeM/16010033**). Besides, this study was also conducted in accordance to the principles of ethics on human research that had enacted by the Declaration of Helsinki during the 18th World Medical Association General Assembly, 1964).

Voluntary written informed consent was acquired from each study participant. They were informed about their rights to withdraw from the study at any stage and for any reason without jeopardizing their subsequent medical care. To protect the confidentiality and anonymity of each study participant, the names of the subjects were not documented in the data collection sheet and each subject received a set of random number produced by the Microsoft Excel random number generator for identification purposes. Apart from that, the data collection sheet were kept by the principal investigator at a secured place and the SPSS file, in which all the research data was stored, was password-protected to prevent any accidental or intentional breach of participant's confidentiality.

To ensure that no subjects were recruited more than the minimum number required to significantly demonstrate the difference in the study outcomes between the 20mg parecoxib + 0.75% ropivacaine and single-agent 0.75% ropivacaine groups, interim analyses were conducted after every 6 subjects recruited. These were done after the number of recruited subjects exceeded 20 subjects per group. Any toxicity or unanticipated harms associated with the study interventions were recorded and reported using JEPeM-USM-FORM 3(G):2014 Adverse Events Report. Opinions from

44

independent study adjudicators which consist of USM ethical review board members were sought to determine whether the trial should be stopped prematurely due to obvious patterns of benefits or harms observed from the interim analyses. If the trial is deemed to be ended prematurely, the date and reason for such early trial termination should be notified to the JEPeM committee using JEPeM-USM-FORM 3(E) 2015.

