THE EFFICACY OF PARECOXIB 20MG AS AN ADJUNCT IN 0.75% ROPIVACAINE IN SUPRACLAVICULAR BRACHIAL PLEUXS BLOCK FOR UPPER LIMB SURGERY

Primary Investigator:	1) DR [name] (MBBS (Manipal), MMed Anaesthesiology (USM))
Co-investigators:	1) DR [name] (MBChB BAO (Queen's University of Belfast), PhD (Newcastle University))
	2) DR [name] (MD (UKM), MMed Anaesthesiology (USM))
	3) DR [name] (MD (USM), MMed Anaesthesiology (USM))
	4) DR [name] (MD (UIA), MSc Medical Statistics (USM))

UNIVERSITI SAINS MALAYSIA

Date of report: 30th NOVEMBER 2017

(Minor amendment: 20th MARCH 2018)

NCT ID: To be assigned

THE EFFICACY OF PARECOXIB 20MG AS AN ADJUNCT IN 0.75% ROPIVACAINE IN SUPRACLAVICULAR BRACHIAL PLEUXS BLOCK FOR UPPER LIMB SURGERY

ABSTRACT

Introduction

Brachial plexus block (BPB) is a critical method in providing anaesthesia for upper limb surgery. Parecoxib, a specific COX-2 inhibitor, has the potential as an adjunct for 0.75% ropivacaine in supraclavicular BP block setting.

Objectives

To investigate whether the efficacy of supraclavicular brachical block is enhanced by the addition of 20 mg parecoxib to 0.75% ropivacaine in patients undergoing upper limb surgery.

Methods

This is a double-blind, active-controlled, parallel group, prospective randomized clinical trial conducted between 20th June and 28th August 2017 involving eighty six (n=86) adults whose age were between 18 and 65 years old, with ASA grade I or II and undergoing various upper limb surgeries whose durations were between 1 and 4 hours. The subjects were block-randomized in 1:1 ratio into two groups; group 1 received adjunct IV parecoxib and 0.75% ropivacaine whilst group 2 received 0.75% ropivacaine alone. The primary end-points are the duration and onset of sensory and motor block and the proportions of complete motor and sensory block at 30 minutes following supraclavicular BP block. The significance of the differences in trial endpoints were statistically tested using Mann-Whitney and Chi-square tests.

Results

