Eighty six (n=86) subjects were randomised to either group and analysed. There were higher durations of sensory and motor blocks in the adjunct parecoxib + ropivacaine group compared to the ropivacaine-only groups (sensory block duration: 6.5 hours vs 5.0 hours, median difference = 1.5 hours, p value <0.001; motor block duration: 4.84 hours vs 3.86 hours, median difference = 0.97 hours, p value <0.001). No significant differences between the two intervention arms with respect to sensory (9 minutes vs 9 minutes, median difference = 0 minute, p value = 0.511) and motor blockades (17 minutes vs 18 minutes, median difference = 1 minute, p value = 0.832) onset. Besides, there no significant difference in terms of complete sensory and motor blockades at 30 minutes post supraclavicular block between parecoxib + ropivacaine and ropivacaine-only groups (sensory blockade at 30 minutes: 100% vs 97.7 %, p value = 1.000; motor blockade at 30 minute = 100% vs 97.7%, p value = 1.000). No adverse events were reported in both intervention arms and the trial was not ended prematurely.

Conclusion

Adjunct parecoxib significantly enhances the durations of sensory and motor blockades, but not their onset and complete sensory and motor block at 30 minutes following supraclavicular brachial plexus block.

(395 words)

SECTION ONE

INTRODUCTION

Brachial plexus block (BPB) has enjoyed ubiquitious popularity for upper limb surgeries (Raju and Coventry, 2013). It provides sufficient anaesthesia for surgical procedures involving upper limbs due to the propinquity of the brachial plexus' trunks and division when they pass the first rib (Gamo *et al.*, 2014).

There are a few common techniques for BPB and one of the most frequentlyutilised one is supraclavicular BPB (Raju and Coventry, 2013). It is not only an efficient mode of anaesthesia intraoperatively, but it is can also provide a quick-onset and dense anaesthesia for surgical procedures that involve the proximal mid-humerus down to the distal hand with excellent safety profile (Raju and Coventry, 2013; Gamo *et al.*, 2014). The supraclavicular block (SCB) is performed above the clavicle and aims at the level of the nerve trunks or division of brachial plexus (BP). Other frequently-employed alternatives include infraclavicular block, interscalene block and axillary BPB (Raju and Coventry, 2013).

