4.2 STUDY PERIOD AND PERIOD OF RECRUITMENT

The total study duration is 10 weeks and the period of patient recruitment is from 20th June 2017 till 28th August 2017.

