4.11 SAMPLE SIZE DETERMINATION

Sample size calculation was performed using Power & Sample Size (PS®) software version 3.1.2 (Dupont and Palmer, Vanderbilt, Nashville, Tenessee, 2014) based on the following outcome parameters:

i) Motor Block Duration –based on Liu et.al, 2013

We are planning a study of a continuous response variable from independent control and experimental subjects with 1 control per experimental subject. In a previous study the response within each subject group was normally distributed with a standard deviation of 139 minutes (Liu *et al.* 2013). If the true difference in the experimental and control means of motor block time is 138 minutes and assuming the attrition (drop-out) rate was 20%, 44 subjects (22 in each intervention arm) were required to reject the null hypothesis that the population means of the experimental and control groups are equal. The type I (α) and type II (β) were fixed at 0.05 and 0.1, respectively and hence the power (1- β) of the study is 0.9.

ii) Sensory Block Duration - based on Liu et.al, 2013

We are planing a study of a continuous response variable from that required 1 control per experimental subject (1:1 control-to-experimental unit ratio). In a previous study, the response within each subject group was normally distributed with standard deviation of 140 minutes (Liu *et al.* 2013). If the true difference in the experimental and control means of sensory block time is 104 minutes and assuming the attrition (drop-out) rate is 20%, we required 39 experimental subjects and 39 control subjects to be able to reject the null hypothesis that the population means of the experimental and control groups are equal with probability (power, $1 - \beta$) of 0.9.The type 1 error probability (α) associated with this test of this null hypothesis is 0.05.

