The level of significance was set at 0.05 and any p value that was less than 0.05 (p < 0.05) is considered significant. The analysis was performed in accordance to the intention-totreat (ITT) principle. A step-by-step summary of statistical methods employed for the analysis of this trial's data is given by figure 4.1 on the next page.

[figure not shown]

Figure 4.1: The step-by-step summary of the statistical methods used in this trial.

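### Section 4.12 describes efficacy looks after every 6 subjects with no endpoint, test or boundary, and six primary endpoints are each tested at 0.05, so the type I error behind the stated 5% cannot be established

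*Combined protocol and SAP*

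**What the plan says.** The interim looks appear only in section 4.12, the ethics section. Their purpose is given as "To ensure that no subjects were recruited more than the minimum number required to significantly demonstrate the difference in the study outcomes", and the schedule as "interim analyses were conducted after every 6 subjects recruited. These were done after the number of recruited subjects exceeded 20 subjects per group". Independent adjudicators drawn from the ethics review board advised "whether the trial should be stopped prematurely due to obvious patterns of benefits or harms observed from the interim analyses". No interim endpoint, test, threshold or maximum number of looks is given.

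Section 4.13 assigns a test to each outcome and adds that "any p value that was less than 0.05 (p < 0.05) is considered significant". It contains no adjustment for repeated looks or for several endpoints.

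The Methods part of the abstract says: "The primary end-points are the duration and onset of sensory and motor block and the proportions of complete motor and sensory block". With sensory and motor counted separately, that is six endpoints. No order is set, although the introduction stresses prolonged duration and section 4.11 sizes the trial on the two durations only, each at 0.05.

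Section 5 reports no look, criterion or interim decision. Section 5.4 says that the trial was not stopped early. The limitations in section 6.4 discuss p values and 90% power, but neither the looks nor the number of endpoints.

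**The concern.** Looks meant to end recruitment at significance are efficacy looks. If each is judged at the final 0.05, a chance excursion at any one of them counts as a finding, and the error rate for that single endpoint rises above 5%. Whether this happened depends on the criterion, which is not stated. Several primary endpoints each tested at 0.05 are a second, separate source of false positives, present even with one final analysis. A reader cannot tell what error rate stands behind a significant result, and a later trial copying this plan would inherit the gap.

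**Working it through.** **Inputs.** Level 0.05 (4.11, 4.13). Sidedness is not stated; I assume two-sided because the null hypothesis is equality of means. Effects and SDs: 138 and 139 minutes (motor duration), 104 and 140 minutes (sensory duration), power 0.90, 1:1 allocation (4.11, 4.10.1). First look: more than 20 per group, so at least 21 per group or 42 in total. Final number: 78 (4.11) or 86 (abstract). Results: Table 5.4.

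**1. The plan's own figures.** n per arm = 2(1.960 + 1.282)²(SD/difference)².
- Motor: 2 × 10.51 × (139/138)² = 21.3, so 22.
- Sensory: 2 × 10.51 × (140/104)² = 38.1, so 39.

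Both agree with section 4.11 ("we required 39 experimental subjects and 39 control subjects"), before any dropout allowance. They describe one uncorrected test of each duration, made once.

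**2. Looks, one endpoint.** Under the null, take the cumulative test statistic at each look and count a rejection if p<0.05 at any of them. Simulated type I error (60,000 or more runs per schedule; the schedules are assumptions):

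| Looks | Analyses | Type I error |
|---|---|---|
| Total 42, 48, … 84, then 86 | 9 | 12.6–12.8% |
| Total 42, 48, … 78 | 7 | 11.5–11.7% |
| Total 48, 54, … 78 | 6 | 10.5–10.6% |
| Per group 21, 27, 33, 39, 43 | 5 | 11.4% |
| Per group 24, 30, 36, 39 | 4 | 9.7–9.8% |
| Per group 26, 32, 38, 39 | 4 | 9.0–9.1% |

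Other criteria give less. Stopping only at p<0.001, with the final test at 0.05, gives 4.9–5.1%. Stopping only when both durations have p<0.05 gives 5.2–7.6% per duration.

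**3. Endpoints, one final analysis.** Four independent time endpoints: 1 − 0.95⁴ = 18.5%. With assumed correlation 0.5 it is 15.5%, and with 0.7 it is 13.4%. The two 30-minute proportions add little: with 43 per arm, Fisher's exact test rejects about 0.1% of the time at a true rate of 97%, and 0.5% at 95%.

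**4. One threshold for both.** Bonferroni over six gives 0.05/6 = 0.0083 per endpoint. Used at each of nine analyses, 0.0083 would run each endpoint at about 2.5%, so it does not cover the looks. The constant level that holds an endpoint at 0.0083 over nine analyses is z = 3.02, or p = 0.0025.

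**5. The reported results.**
- Sensory duration: U = 199, null mean 43 × 43/2 = 924.5, SD √(43 × 43 × 87/12) = 115.8, z = (924.5 − 199)/115.8 = 6.27, p about 4e-10.
- Motor duration: t = 6.561 on 79.342 df, p about 5e-9.

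Both are far below 0.0025.

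**6. A single bounded look.** Lan-DeMets O'Brien-Fleming-type spending at 42/86 = 0.488 of the information gives z = 3.002 (p<0.0027) at the look and z = 1.968 (p<0.049) at the end. For sensory duration, d = 104/140 = 0.743, so the expected z is 0.743√(21/2) = 2.41 at 42 subjects and 0.743√(43/2) = 3.44 at 86. By normal approximation, power at 86 is Φ(3.44 − 1.96) = 93.1% with no look, and the same to within 0.1 point with it. The chance of crossing at 42 is Φ(2.41 − 1.96) = 67% at p<0.05, against Φ(2.41 − 3.00) = 28% at p<0.0027.

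**The case against.** The case for leaving this alone is substantial. The trial was not stopped early. The adjudicators were independent and may have asked for far more than p<0.05. The 0.05 is stated per test, with no family-wise claim to break. The introduction and sample size already give weight to the durations. The onset and 30-minute results are null, so no significant primary result depends on the missing control. Figures 4.1 and 4.2 and the pages after the first part of the case report form are not in the text reviewed, and might hold a rule.

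Most of that stands, and it limits the consequence for this trial to disclosure. It does not close the gap. Error control depends on the rule that would have stopped the trial, and a run to full length does not reveal that rule. Emphasis on the durations is not a formal order, and the abstract calls all six endpoints primary.

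Three stronger readings are tempting but unsupported.
- A reader might infer that the error rate was in fact doubled. That needs p<0.05 as the criterion, which the documents do not state.
- A reader might infer that the duration findings are unsafe. Step 5 shows that they are not.
- A reader might infer the criterion from the final number, since "Eighty six (n=86) subjects were randomised to either group and analysed" against 78 sized. Section 4.2 fixes the recruitment dates ("The total study duration is 10 weeks"), section 4.6 cites a thesis deadline, and section 5.4 says that the trial ran its planned length. The count therefore says nothing about the stopping rule.

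**Conclusion.** The concern holds as a gap in the plan and its reporting. The efficacy looks have no stated rule. If p<0.05 on one endpoint was the criterion, that endpoint's type I error was about 10–13% (looks every 6 in total) or about 9–11% (every 6 per group). If the criterion was much stricter, it was near 5%. Separately, the four time endpoints carry a 13–19% chance of at least one false positive at a single final analysis, for assumed correlations from 0.7 to 0. These figures assume two-sided tests and the schedules shown, and the finding is limited to the visible text. The conclusion on both durations does not change.

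**What to change.** 1. **Section 4.12, for any trial run from this plan.** Replace the open-ended looks with harm monitoring only, or with one efficacy look on a named endpoint under a Lan-DeMets O'Brien-Fleming-type boundary (at 42 of 86: p<0.0027, final p<0.049). This costs almost no power. The price is the lower chance of early stopping in step 6, 28% instead of 67%.
2. **Section 5, for this trial.** Keep 0.05 as the level actually used. Report how many looks were made, when, on which endpoint, by what criterion and with what decision, or state that none were made.
3. **Section 5, post hoc check, labelled as such.** Apply one threshold covering looks and endpoints: about p<0.0025 for up to nine analyses and six endpoints. If no looks were made, use Bonferroni at 0.0083, or Holm. Note that six is the abstract's count. Both durations pass. Do not choose an endpoint order now that the results are known.
4. **Section 6.4.** Add the looks and the number of endpoints to the limitations, and say that the 90% power refers to a single uncorrected 0.05 test of each duration.

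Items 2 to 4 cost some text, no patients and no conclusion. I would not write a six-way correction into the plan as a default. At 43 per arm it would cut sensory-duration power in a later trial from 93% to 79% with Holm or 77% with Bonferroni, a trade-off that can reasonably be argued either way.

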4.13 STATISTICAL ANALYSIS

All analysis was implemented using the Statistical Package for Social Science (SPSS) for Windows version 20 IBM Corp. Released 2011. IBM SPSS Statistics for Windows, Version 20.0. Armonk, NY: IBM Corp) and STATA version 11 (StataCorp. 2009. Stata Statistical Software: Release 11. College Station, TX: StataCorp LP).

The data was firstly assessed for any inaccurate data entry and missing data. The data was cross-checked with the information in data collection sheet to optimise accuracy of data entry. Multiple imputation was then utilised as remedial measures to rectify and mitigate the effects of missing data on the accuracy of subsequent analyses. Besides, missing data were treated as missing at random (MAR) based upon Rubin's missing data mechanism (Little and Rubin, 2002).

Numerical data was then descriptively summarised in mean and standard deviation (or median and interquartile range if the data were not normally distributed) whilst frequency and percentage were the descriptive summaries for categorical data. For continuous outcome variable, the normality of each outcome variable was then **subjectively** evaluated by histogram with overlying normal distribution curve, box and whisker plot and stem and leaf diagram. Besides, Shapiro-Wilks (since the sample size is small, i.e. less than 50) was also utilised to provide **objective assessments** of normality assumption. Any significant p-value (p<0.05) indicates that the normality (Gaussian) assumption had been violated. These assessments were then further strengthened by the

objective evaluation of the normality assumption using Fisher's coefficient of skewness, whose formula is presented as follows:

Fisher's coefficient of skewness = Skewness / standard error of skewness

The level of significance was set at 0.05 and any p value that was less than 0.05 (p < 0.05) is considered significant. The analysis was performed in accordance to the intention-totreat (ITT) principle. A step-by-step summary of statistical methods employed for the analysis of this trial's data is given by figure 4.1 on the next page.

[figure not shown]

Figure 4.1: The step-by-step summary of the statistical methods used in this trial.

4.14 TRIAL FLOW CHART

[figure not shown]

Figure 4.2: The flowchart of this study (prepared according to the CONSORT guideline).

SECTION FIVE

STUDY RESULTS

5.1 THE CLINICO-DEMOGRAPHIC PROFILES OF THE STUDY PARTICIPANTS

[figure not shown]
On the whole, 86 study participants were included in the analysis. The mean age and weight of the participants are similar between the two groups of interventions. Apart from that, both intervention groups exhibit similar patterns of VRS pain score, volumes of local anaesthetics received, supplemental local anaesthetics received and PCA morphine profiles.

With regards to gender and ethnic compositions, both intervention groups, in general, demonstrated similar proportions of females, males and each ethnic groups. Furthermore, both intervention arms have also relatively the same proportions of participants for each ASA grade. Nevertheless, with respect to the specific surgical sites, more study participants in the ropivacaine group had surgeries to their arms whilst more patients in the combined parecoxib-and-ropivacaine group had surgeries to their forearms. Besides, there are also two missing data in this group. However, it can be safely said that proportions of surgical sites are roughly similar in both groups. For further information, refer to table 5.1 and figures 5.1-5.3.

Parameters 1	Parecoxib + Ropi Mean (SD)	vacaine (n=43) n(%)	Ropiva Mean (SD)	caine (n=43) n(%)
Age	43.8 (13.7) 47.5 (26) ^a		46.3 (12.6) 51.0 (21.0) ^a	
Weight (kg)	60.8 (7.6) 60.0 (13.0) ^a		61.6 (7.6) 60.0 (12.0) ^a	
VRS pain score	1.0 (0)		1.0 (0)	
LA volume	20.0 (0)		20.0 (0)	
Supplement LA volume	0.0 (0)		0.0 (0)	
Time to 1 st PCA morphine (hours)	0.0 (0)		0.0 (0)	
PCA Morphine deman within 24 hours (count			0.0 (0)	
PCA Morphine given within 24 hours (count	0.0 (0) s)		0.0 (0)	
Gender Female Male		16 (37.2) 27 (62.8)		0 (46.5) 3 (53.5)
Ethnicity				
Malay Chinese Others		42 (97.7) 1 (2.3) 0 (0)	۷	41 (95.3) 1 (2.35) 1 (2.35)
Surgical sites Forearm Arm Hand Fingers Missing		14 (32.5) 21 (48.9) 0 (0) 6 (14.0) 2 (4.6)		$\begin{array}{cccc} 8 & (18.6) \\ 31 & (72.1) \\ 1 & (2.3) \\ 3 & (7.0) \\ 0 & (0) \end{array}$
ASA grades I II		7 (16.3) 36 (83.7)		6 (14.0) 37 (86.0)
Preoperative VRS scor ^a Median (Interquartile range			0.0 (0.0)	

Table 5.1: The clinico-demographic characteristics of study participants (n = 86)

^aMedian (Interquartile range)

[figure not shown]

Figure 5.1 (a-b): The proportions and percentages of subjects in each intervention arm, as stratified by gender and ethnicity of subjects

[figure not shown]

Figure 5.2 (a-c): The proportions and percentages of ASA grades, sensory and motor block status at 30 minutes post BPB as stratified by the intervention arms.

[figure not shown]

Figure 5.3: Pie charts detailing the percentages of subjects in each intervention arm as stratified by the surgical sites.

5.2 THE STATISTICAL EVALUATIONS OF THE NORMALITY AND HOMOGENEITY OF VARIANCES ASSUMPTIONS FOR CONTINUOUS OUTCOME VARIABLES

Based on the results presented in table 5.2 and figures 5.4 - 5.9, it can be conspicuously observed that all continuous outcome variables have violated the normality (Gaussian) assumptions. This claim is corroborated by the significant Shapiro-Wilks test results for the all outcome variables and the large values for the a significant proportion of Fisher's coefficients of skewness. Besides, based on the inspection of figures 5.4 - 5.9, all of the histograms with the overlying distribution curves do not conform to the bellshaped characteristic of normal distributions and exhibit extreme skewness with or without "peaked" (leptokurtic) or flat (platykurtic) at the symmetrical point. This fact is further augmented by the uneven lengths of box parts of the box plots when comparisons were made with their whiskers. All these are tell-tale signs of distributions that have violated the characteristics of normal distribution curves.

On the other hand, the homogeneity of variances assumption is deemed fulfilled for the majority of continuous outcome variables since the p values for the Levene's tests are not significant. However, for motor block duration, the p value is significant, indicating that the homogeneity of variances assumption is not tenable. We can conclude for this variable, the variances are inhomogeneous between the two intervention groups (i.e there is a heteroscedasticity in the variances).

From these results, we conclude that the appropriate statistical test is Mann Whitney test for all continuous outcome variables, except for motor block duration (in this case, the Welch's version of the independent t-test is the most suitable alternative).

55

Parameters	Shapiro-Wilks test		Fisher's Skewness Coefficients		
	Par+Ropi ^b	Ropivacaine	Par+Ropi ^b	Ropivacaine	
Age	< 0.001	< 0.001	1.04	-2.58	
Weight	0.019	0.003	1.56	-0.31	
Sensory block onset	<0.001	0.001	2.61	2.70	
Motor block onset	0.001	<0.001	-1.01	-0.84	
Sensory block duration	0.001	0.001	1.62	0.13	
Motor block duration	<0.001	< 0.001	0.69 ^a	-1.29	

Table 5.2: The objective statistical tests for the evaluation of the assumption of normality

^aKurtosis (peakness of the distribution) indicates normality assumption is violated. ^bParecoxib + Ropivacaine

Table 5.3: The results of Levene's tests for assessing the homogeneity of variances assumption

Parameters	F statistics	p values	
Age	1.239	0.269	
Weight	0.064	0.801	
Sensory block onset	0.003	0.957	
Motor block onset	2.000	0.161	
Sensory block duration	0.517	0.474	
Motor block duration	7.564	0.007	

[figure not shown]
[figure not shown]

Figure 5.4: The histograms (with the overlying distribution curves) and box plots representing the characteristics of distribution for age.

[figure not shown]

Figure 5.5: The histograms (and the overlying distribution curve) and box plots representing the distribution of weights of patients.

[figure not shown]

Figure 5.6: The histograms (with the overlying distribution curves) and box plot of the time of onset of sensory block as stratified by the intervention arms. The circles and numbers represent outliers and outlier's ID.

[figure not shown]

Figure 5.7: The histograms (with overlying distribution curves) and box plots representing the time of onset of motor block as stratified by the intervention groups.

[figure not shown]

Figure 5.8: The histograms (with the overlying distribution curves) and box plots for the duration of sensory block as stratified by the intervention groups.

[figure not shown]

Figure 5.9: The histograms (with the overlying distribution curves) and box plot representing the duration of motor block as stratified by the intervention groups. The circles and numbers indicate outliers and outlier's ID, respectively.

